4.2 SCIENTIFIC RATIONALE FOR STUDY DESIGN

The control intervention will meet the requirements for a comparison control for testing behavioral interventions¹²⁵, which are equivalent in contact time, credible and interesting, and exert limited treatment effects.

5 STUDY POPULATION

Sixty participants (~30 early adolescents with asthma and 30 caregivers of early adolescents with asthma) will take part in pre-trial focus groups. 85 dyads and 8 primary care providers (PCPs) will participate in the trial. Post-trial interview will be conducted. We will do post-trial interviews with a purposive sample of ~6 participating clinicians, ~10 patient participants, and ~10 caregivers.

5.2 EXCLUSION CRITERIA

Exclusion criteria across the study are: 1) serious mental health conditions (caregiver and/or child) or developmental delays (child) that preclude completion of study procedures or confound analyses. Focus group participants will NOT be eligible to participate in the pilot.

5.3 SCREEN FAILURES

Screen failures are defined as participants who consent to participate in this study but are not subsequently assigned to the study intervention or entered in the study. Individuals who do not meet the criteria for participation in this trial (screen failure) because of meeting one or more exclusion criteria that are likely to change over time may be rescreened.

5.4 STRATEGIES FOR RECRUITMENT AND RETENTION

AIM 1: FOCUS GROUPS

Recruitment of participants. We will recruit using three methods.

(1) *Opt-out Letter:* The FQHC administrator/data analyst at each site will create a list of potential participants using a combination of ICD-10 Asthma 493-specific queries of electronic membership records, age, and prescription profile. As in our BREATHE trial, we will employ IRB-approved opt-out letters signed by the federally-qualified health center (FQHC) medical director and mailed to all potential participants. The opt-out letter will identify two active responses and one passive option. The active responses include requesting not to be contacted or calling the research team directly to request screening. The passive response allows the research team to contact the patient if they have not responded within the specified timeframe (i.e., 2 weeks from letter receipt). CU staff will be provided the contact information of eligible patients who were sent letters and did not actively opt out; CU staff and/or UHP staff will then call families to recruit them, explaining the study and collecting consent from those who wish to participate.

(2) *UHP Provider/Staff Referral:* UHP providers and staff will explain the study to eligible dyads who present at the clinic on a given day; they will either consent interested families or refer them to CU staff for consent. UHP may also call their patients; interested patients can be consented orally following the already IRB approved oral script for consenting, or if granted permission to share the caregiver's contact information with CU, pass their information to CU staff who will consent orally using the approved oral consent script.

(3) *Self-referral:* We will also accept participants who respond to recruitment materials. UHP staff will post and/or distribute IRB approved flyers and include the IRB approved slide summarizing the study in their electronic advertising at the clinics; interested patients will contact the CU staff to learn more about the study. Interested families can be consented orally using the approved oral consent script, or in person at the clinic if they have an upcoming appointment.

AIMS 2 & 3: TRIAL

Recruitment of primary care provider (PCPs) participants for pilot trial

Enrolling 8 PCPs participants to the trial. We will recruit 4 primary care providers (PCPs) per site. The clinic will identify PCP participants and trained CU staff will complete a written consent form if done in person or an verbal consent if done orally over the phone. The participating sites have 5 to 14 PCPs who manage a panel of pediatric asthma patients.

Enrollment feasibility

We will enroll 30 dyads (caregiver-child) for focus groups and 85 dyads for the trial (trial dyads cannot have participated in focus groups).

Aim 1: Focus Groups: Participants will be informal caregivers (e.g., parent, grandparent, older sibling) and children (ages 10-14) with physician-diagnosed asthma.

Aims 2 & 3 Clinical Trial – Dyads: We will enroll early adolescents, informal caregivers and primary care providers. Early adolescents (ages 10-14) will have physician-diagnosed asthma (and screen positive for uncontrolled asthma as measured by the Asthma Control Questionnaire. Caregivers will be informal caregivers (e.g. parent, grandparent, older sibling). Primary care provider participants will be eligible if they manage a panel of pediatric patients.

Data provided by Urban Health Plan Inc. indicates that they follow a panel of 1,896 children aged 10-14 with asthma who are prescribed controller in the past year; of these 596 have uncontrolled asthma as indicated by an asthma control test score administered at their last appointment. Considering our 60% success rate for enrolling dyads in our previous trial, this would yield 358 dyads for enrollment (we need only 30 dyads for focus groups and 40 dyads for the trial).

Aims 2 & 3 Clinical Trial – PCPs: Based on the strong FQHC support for this project and the fact that in our pilot BREATHE study, all PCPs approached agreed to participate, we do not anticipate difficulty in recruiting PCPs. Moreover, we will replace a PCP should a PCP decline to enroll or drops out before end of study; we have a sufficiently large waitlist of PCPs (and additional sites) from which to replace PCPs, if needed.

Vulnerable Subjects

Asthma's impact is significant among minority populations. Erroneous beliefs impede asthma control. To date, community-based asthma interventions have not reduced the burden of asthma. For this reason, we adapted an evidence based brief SDM intervention used in acute care settings to FQHC settings with input from black adult asthma patients and their loved ones. We will develop this intervention by adapting our prior work in our adults which found several positive short-term effects on asthma control, SDM, and symptom burden.

Pregnant women will be eligible to participate since improving asthma control for their early adolescent children would benefit the family.

Retention of patient participants

UHP has retained 72-90% of participants in clinical trials requiring data collection of 12 months (Personal communication, [name]). To retain 80% of dyads over 3 months post-intervention for this trial, we will use the retention strategies proven successful in our previous trials in FQHCs requiring 3+months of follow-up:

1. Assigning one Research Assistant (RA) to a dyad: Data collection by RAs that have a history of working at these FQHCs will facilitate rapport and retention. RAs are often members of the community; all have received training on the delivery of patient-centered care.
2. Confirming contact information at each assessment; obtaining contact information of two or more people who will know how to contact the participant: We will update contact information (e.g., name, address, phone numbers, emails) for the participants and two or more of their contacts at each study visit; participants will be asked to indicate preferred mode of communication (email, text or phone).
3. Frequent data collection points: There are 4 assessment points over the 3-month follow-up. Participants will receive monthly communication from our study team to confirm upcoming visits. If they fail to respond after three attempts using multiple modes of contact over varying day/evening hours and weekday/weekend attempts, we will contact their alternative contacts.
4. Graduated incentives: Participants will be compensated using a graduated incentive plan. We will pay the dyad: baseline=\$25; 1-month=\$30; 2-month=\$40; 3-month=\$50 (total \$145). A portion of each incentive will be made directly to the child.

Retention of PCP participants

Since we have FQHC administrative buy-out of PCP time and strong support for this project and because each PCP delivers the intervention only one-time to small number of their patients , we do not anticipate difficulty with PCP retention. We will replace a PCP should a PCP drop out and we have a sufficiently large waitlist of PCPs (and additional sites) from which to choose, if needed.

6 STUDY INTERVENTION(S) OR EXPERIMENTAL MANIPULATION(S)

6.1 STUDY INTERVENTION(S) OR EXPERIMENTAL MANIPULATION(S) ADMINISTRATION

6.1.1 STUDY INTERVENTION OR EXPERIMENTAL MANIPULATION DESCRIPTION

DESCRIPTION OF STUDY INTERVENTIONS.

BREATHE-PEDS Intervention. BREATHE, grounded in shared decision-making (SDM) theory and developed with input from black adults with asthma, utilizes PCPs to deliver a brief intervention using motivational interviewing in a single brief (9-minute) intervention during an office visit. Using data we collect from our focus groups we will develop **BREATHE-Peds** by adapting BREATHE. PCPs follow a 4-step script developed in partnership with patients and tailored to specific erroneous beliefs measured by the Conventional and Alternatives Management for Asthma (CAM-A) survey, as well as to their Asthma Control Questionnaire (ACQ) score. A lab coat pocket-sized laminated action card will supplement the

web-based application that the PCPs follow prompting them through the intervention. The tailored script is automatically generated based on the RA inputting the CAM-A and ACQ responses. We will randomize providers to one of two intervention arms. Neither intervention alters the clinical care study participants receive. Our intervention involves training providers on communication methods/topics; it does not involve our changing or modifying patient medication in any way. Patients in both arms receive the same asthma care from the providers.

- Step 1: Raise the subject (1½ minute). PCP establishes rapport using persuasive communication techniques and assesses the dyad's asthma knowledge, perception of asthma control, quality of life, self-care preferences, and motivation for enhanced asthma control, exploring specific asthma and ICS beliefs that they have endorsed and that are known to be associated with uncontrolled asthma.
- Step 2: Provide feedback (1½ minutes). PCP provides feedback to the dyad based on assessments made in the prior step. The PCP candidly discusses the patient's uncontrolled asthma and erroneous beliefs in the context of gaps in asthma self-management, drawing a connection between current self-management and uncontrolled asthma.
- Step 3. Enhance engagement (3 minutes). The PCP attempts to enhance the dyad's motivation to increase Self-management using motivational interviewing techniques such as collaboration, empathy, concern, and acceptance of ambivalence about self-care. In this step, the PCP may elicit the dyad's beliefs regarding the benefits, and negative sequelae, of their current degree of self-management (pro/con).
- Step 4: Shared decision-making (3 minutes). The PCP and dyad jointly consider treatment options. The PCP will actively attempt to build consensus around self-management, reconciling conflicts to better align asthma and ICS beliefs with evidence-based guideline-directed treatment. For example, if the patient uses ICS intermittently (rather than twice daily as required) because of an erroneous belief that tolerance to ICS develops with daily dosing, then the PCP will attempt to counter that belief using the tailored script, as well as information from national asthma guidelines. This will likely include encouraging the patient to use ICS once a day (50% adherence) as an initial short-term plan to be followed by a return visit and re-evaluation of asthma control. If the patient declines to engage in SDM or declines attempts at negotiating ICS use, then the PCP and the patient agree to disagree.

Dose-matched Attention Control Intervention. The control intervention will meet the requirements for a comparison control for testing behavioral interventions, which are equivalent in contact time, credible and interesting, and exert limited treatment effects. Control participants will receive a PCP-led 9-minute scripted discussion tailored to healthy lifestyles (e.g., diet, exercise) following Teach to Goal principles:

- Review of weight, diet and exercise: (3 minutes). PCP and patient review current weight/fitness, current diet and/or current exercise in the context of goal-setting.
- Exercise counseling: (3 minutes). PCP describes benefits of exercise and options for starting/increasing exercise.
- Plan for goal attainment (3 minutes). PCP explores barriers and facilitators to goal attainment.

Control PCPs will use study the web-based app to access the healthy lifestyle scripts and patient participant's ACQ score but will not have access to CAM-A results or **BREATHE-PEDS** scripts. While control participants will receive important nutrition and lifestyle information, the control intervention is not designed to be specific enough to change strategies related to ICS adherence. Further, the control group offers a similar format as BREATHE-PEDS, namely PCP-led discussions in which PCPs use tablets to review ACQ scores and initiate a tailored discussion.

6.2 FIDELITY

6.2.1 INTERVENTIONIST TRAINING AND TRACKING

Intervention Training, Supervision and Fidelity. We have extensive experience training clinicians to deliver interventions, as well as monitoring treatment fidelity. Procedures used in this study will mirror established procedures employed in our BREATHE-PEDS pilot.

- BREATHE-PEDS Training. The core training for PCPs delivering the **BREATHE-PEDS** intervention will be conducted by our consultant, [name], and will consist of one, 2-hour instructional session comprised of: didactics - 30 minutes; role-playing common clinical scenarios - 10 minutes; SDM role-playing - 50 minutes; question & answers – 30 minutes. Immediately after training, PCPs will be tested using a standardized patient scenario to demonstrate that he/she can deliver the intervention in 9 minutes or less, the average length obtained in our feasibility trial. If the PCP fails to achieve 100% proficiency, she/he will receive additional instruction and retested. Prior studies demonstrated that remediation re-training results in 100% proficiency.
- Attention Control Training. PCPs assigned to the attention control condition will be trained using a 15-minute self-guided instructional manual followed by an in-person question and answer period with the PI.
- Supervision and fidelity. We will audio record all participants' intervention) visits (**BREATHE-PEDS** and control). The Research Assistant (RA) will set up two digital recorders at the beginning of the visit and upload audio files to a secure HIPAA-compliant site within 24 hours of the visit. Within 24 hours of recording, files will be uploaded and 2-3 trained raters, working independently of one another, will review the sessions. We will evaluate fidelity the first time a PCP delivers their intervention and then at ~20% of randomly selected visits, a protocol successfully used by the consultant. At least one additional file per PCP will be reviewed prior to enrollment of their 5th participant, to evaluate drift and the length of sessions. For **BREATHE-PEDS** we will determine whether the critical elements of the brief intervention were completed in 9 minutes using the validated Brief Negotiation Interventions Adherence Scale adapted to asthma. For the control sessions, raters will note the length and content of the healthy lifestyle discussion. Within 24 hours of the rating, the PCPs will receive a summary of their performance (free of personal health identifiers) via email. PCPs will receive additional training to enhance intervention fidelity and dose (length) if problems are identified (by [name] for **BREATHE-PEDS** group and [name] for control group). PCPs will not be excluded from the study if they fail to deliver all elements of their respective intervention. PCPs will not be excluded if they require more (or less) than 9 minutes to deliver the intervention. Control PCPs will not be excluded if they teach asthma self-care; these metrics will be tracked.

6.3 MEASURES TO MINIMIZE BIAS: RANDOMIZATION AND BLINDING

DESCRIPTION OF RANDOMIZATION PROCEDURES: Prior to trial initiation, all eligible clinicians will be randomized equally into the BREATHE and the attention control condition stratified for provider type, using a computer-generated randomization list. We will obtain informed consent from the first eight clinicians on the randomization list: four/site; two physicians and two nurse practitioners [NPs]

randomized to BREATHE; two physicians and two NPs randomized to control. Those remaining on the list will be placed on “standby” if replacement is needed.

CONTAMINATION.

Contamination will be minimized by (1) training only **BREATHE-PEDS** clinicians to deliver the active intervention and (2) encouraging confidentiality regarding training and intervention content.

MASKING.

Dyads, data collectors, and the statistician will be blinded to assignment. Consent materials will inform dyads that the focus of the trial is on the communication they have with their clinician about asthma management and control. Immediately after the intervention, dyads will be asked to guess the condition to which their clinician had been randomized. At the end of participants’ final data collection visit, data collectors will be asked to guess whether participants had received the active or control intervention at the visit. These data will provide some measurement of the success of masking.

7 STUDY INTERVENTION/EXPERIMENTAL MANIPULATION DISCONTINUATION AND PARTICIPANT DISCONTINUATION/WITHDRAWAL

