Aim 2: Post-Trial Interviews. The PI will conduct post-trial semi-structured interviews with a purposive sample of ~6 participating clinicians, ~10 patient participants, and ~10 caregivers to ascertain their satisfaction with, and acceptability of, the active and control interventions. As part of our implementation evaluation, attempts will also be made to interview patient participants and PCPs who withdraw from the study (or PCPs who decline to enroll, if we have any), to better understand what it was that prevented their continued participation.

RANDOMIZATION.

We will randomly assign all eligible clinicians equally into the **BREATHE-PEDS** and the dose-matched attention control condition stratified for provider type (physician vs. nurse practitioner [NP]/physician assistant [PA]) using a computer-generated randomization list in advance of the trial. The first four physicians and first four NPs/PAs in each condition (**BREATHE-PEDS** and control) will then be invited to enroll (N=8). Those not selected (i.e., those remaining on the list) will be placed on "standby" if a replacement is needed. Invited PCPs signing consent will then be trained on the condition to which they were randomized. Each PCP will then enroll ~10 dyads meeting inclusion/exclusion criteria (N =85).

STATISTICAL ANALYSES.

Development and Intervention Feasibility. We will document recruitment, randomization and retention success, as well as process and implementation assessments.

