9.2 SAMPLE SIZE DETERMINATION

Power & Sample Size. With a sample size of 10 patients/PCP and 4 PCPs in each intervention arm (total $n=10*4*2=80$), and 20% attrition, we calculated the power to test the effect of intervention on outcomes. Power calculations were based on: (1) 4 repeated observations over the 3-month follow-up with a correlation of $p=0.8$ between repeated measures; (2) intra-cluster correlation among PCPs=0.2 to account for clustering of patients from the same PCP; and (3) LMMs to estimate pre- and post-intervention differences. We estimated an 80% power to detect a small effect size ($d=0.15$). For ACQ, this is equivalent to detect a post-intervention difference of 0.15 (assuming $SD=0.9$).

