9.4.2 ANALYSIS OF THE PRIMARY AND SECONDARY ENDPOINT(S)

Analytic Plan.

Aims 1 & 2: Development and Intervention Feasibility. We will document our success in meeting recruitment and randomization goals, as well as process (recruitment outreach and numbers meeting eligibility criteria who accept or decline enrollment) and implementation assessments (retention rates, data completion rates, as well as fidelity, contamination and masking in the clinical trial arm).

Randomization. This is a group-randomized trial in which the primary care providers (PCPs) will be randomized within sites to the active and control conditions. We will utilize a stratified block randomization plan, stratifying by provider type (physician vs. nurse practitioner/physician assistant), to insure equal numbers of PCPs within each PCP type are assigned to each condition. Randomization lists will be computer-generated in advance by our biostatistician. Outcomes will be analyzed at the level of the early adolescent and/or caregiver.

Masking. Participants and data collectors will be masked to study hypotheses and group assignment; the investigators will be blinded to group assignment. PCPs in both intervention conditions will use tablets as part of their respective interventions and have sessions audio-recorded, facilitating masking of participants and data collectors.

Aim 3: Intervention Effects. Intervention effects will be assessed using linear mixed models (LMM) or generalized linear mixed models (GLMM) for continuous and categorical outcomes, respectively. All hypothesis tests will be two-sided at level $\alpha=0.05$. The key outcome will be ACQ score; secondary measures will be examined to inform the future RCT. Separate models will be fitted for different outcome measures. If y_{ijt} is the outcome for patient j of provider i at time t , without loss generality then the following LMM will be used:

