$y_{ijt} = \beta_0 + \beta_1 * \text{Group} + \beta_2 * t + \beta_3 * \text{INT} + \beta_4 * X_{ij} + \mu_i + \mu_{ij} + \varepsilon_{ijt}$, where group, t , and INT are design variables. Group is an indicator for intervention arm and INT is an indicator for pre- or post-intervention. X_{ij} is a vector of possible PCP- and patient-level covariates. The random term $\mu_i \sim \text{N}(0, \sigma_1^2)$ is a PCP-specific random effect and $\mu_{ij} \sim \text{N}(0, \sigma_2^2)$ is a patient-specific random effect; $\varepsilon_{ijt} \sim \text{N}(0, \sigma_\varepsilon^2)$ is the model random error. To examine the effect of intervention on the outcome, we will conduct hypothesis test of $H_0: \beta_3 = 0$. We will explore differential intervention effect by sex.

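### Sections 4.1 and 6.3 stratify provider randomisation by provider type only, while section 9.4.2 says it is done within sites; one scheme should be fixed before the list is drawn

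*Combined protocol and SAP*

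**What the plan says.** - **Section 6.3** states that "all eligible clinicians will be randomized equally into the BREATHE and the attention control condition", "stratified for provider type, using a computer-generated randomization list". It then consents the first eight on the list, four per site, with two physicians and two nurse practitioners in each arm. Replacements come from a standby list that is not tied to a site.
- **Section 4.1** also stratifies by provider type alone and does not mention site.
- **Section 9.4.2** says that PCPs "will be randomized within sites to the active and control conditions", by stratified blocks, and names provider type as the only stratification factor.
- **The model** (4.1 and 9.4.2) has terms for group, time and a pre/post indicator, with random effects for PCP and patient. The remaining term "is a vector of possible PCP- and patient-level covariates". Provider type is not required and site is not named.
- **Size.** Section 9.2 plans "With a sample size of 10 patients/PCP and 4 PCPs in each intervention arm", and section 5.1 places four PCPs at each of two sites. The synopsis, however, lists three recruiting sites. Section 4.1 invites four physicians and four NPs/PAs per condition, which makes 16, although it gives the total as 8.

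**The concern.** A statistician building the list could follow either rule. Under 4.1 and 6.3 the quota of four per site fixes how many PCPs each clinic supplies. It does not fix how many of them are in each arm. Every quota in 6.3 can be met with the arms split 3:1 between clinics, and under some provider mixes 4:0.

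With eight randomised units, chance cannot be relied on to even this out. The PCP random effect does not remove a clinic imbalance, because it models scatter among PCPs and not a shared shift at one site. Provider type, the one stratum that all three sections agree on, may also be left out of the model, and that affects the size and power of the test.

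**Working it through.** **1. Layout.** Section 6.3: (2 physicians + 2 NPs) × 2 arms = 8 PCPs. Section 5.1: 4 per site × 2 sites = 8. Section 9.2: 10 × 4 × 2 = 80 dyads. These agree with each other. The steps below take eight PCPs and two sites as given.

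**2. Chance of an unequal split under 4.1 and 6.3.** Two of four physicians and two of four NPs/PAs go to the active arm without regard to site: C(4,2) × C(4,2) = 6 × 6 = 36 equally likely allocations. The documents do not give the provider mix per site, so three mixes are shown.

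| Mix (site A; site B) | Balanced 2:2 | Split 3:1 | Arm identical to site |
|---|---|---|---|
| 2 physicians + 2 NPs/PAs; the same | 18/36 (50%) | 16/36 (44.4%) | 2/36 (5.6%) |
| 3 + 1; 1 + 3 | 18/36 (50%) | 18/36 (50%) | 0 |
| 4 + 0; 0 + 4 | 36/36 (100%) | 0 | 0 |

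In the first row, the number of active-arm PCPs at site A is 0, 1, 2, 3 or 4 in 1, 8, 18, 8 and 1 allocations. The chance of any unequal split is (1 + 8 + 8 + 1)/36 = 50%.

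**3. Effect of a split.** Let D be the true clinic difference in the analysed outcome. Shift in the arm contrast = (share of active PCPs at site A − share of control PCPs at site A) × D.

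- 3:1 split: (3/4 − 1/4) × D = 0.5D. Fitting site removes this, at a variance factor of 1/(1 − 0.5²) = 1.33.
- Arm identical to site: (1 − 0) × D = D, and no model can separate the two.

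D is not in the documents. For an assumed D of 0.1 to 0.5 ACQ points, a 3:1 split shifts the contrast by 0.05 to 0.25. At D = 0.3 the shift is 0.15, the target difference in section 9.2. If ACQ is analysed as change from baseline, D is the clinic difference in change and not in level.

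**4. Which outcomes are exposed.** In the section 8 schedule, ACQ has a baseline. SDM-Q-9 is taken only immediately after the visit, and exacerbation only at months 1 to 3. The synopsis does describe oral steroid use from one year before the intervention, so part of the exacerbation endpoint may have earlier data.

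**5. Randomising within site × type.** With two physicians and two NPs/PAs per site, every allocation puts two active and two control PCPs at each site. The chance of imbalance is 0%.

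**6. Leaving provider type out of the model.** Consider eight PCP means: 2 arms × 2 types × 2 PCPs. If the types differ by δ, the unadjusted residual sum of squares gains 4 × (δ/2)² = δ² in each arm, or 2δ² over 6 df. The expected variance estimate is then σ² + δ²/3, which is 1.33σ² at δ = σ. The true variance of the arm contrast is unchanged, because type is balanced between arms, so the test is conservative. Simulation, with a true effect of 2 SD of PCP means for power:

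| Type difference | Type omitted (6 df) | Type fitted (5 df) |
|---|---|---|
| 1 SD of PCP means | size 2.9%, power 54% | size 5.0%, power 62% |
| none | power 66% | power 62% |

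The effect used here is for illustration only. With ICC 0.2, 10 dyads per PCP and SD 0.9 (section 9.2), one SD of PCP means is 0.9 × √(0.2 + 0.8/10) = 0.48 ACQ points. Two SD is about 0.95 points, far above the planned 0.15.

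**The case against.** A reader might infer that neither the design nor the analysis protects against a site imbalance. The documents do not support that. Section 9.4.2 has its own randomisation paragraph and says allocation is within sites, by stratified blocks. If it is implemented with balance in each site and type, no imbalance arises. Sections 4.1 and 6.3 are silent on site and do not say that it is ignored. What stands is that 6.3, which describes the procedure, omits the safeguard.

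A reader might also infer that a site split moves the whole arm contrast. That is true only of complete confounding, which is at most 5.6% in the mixes examined.

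Chance imbalance is not systematic bias either. Averaged over the 36 allocations, with an assumed clinic difference of 1 SD of PCP means and no adjustment, the simulated false-positive rate is 5.5% for the 2 + 2 mix and 4.7% for the 3 + 1 mix. At 2 SD it is 7.1% and 3.8%. The harm is to the estimate in the one allocation actually drawn. The documents give no clinic difference, all sites belong to one organisation, and this is a feasibility trial.

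For the primary outcome, a stable clinic difference cancels in a change-from-baseline contrast. This stands, with one reservation: the tested coefficient is that of a pre/post indicator, so a between-arm contrast in change is not yet written down. That is a separate matter.

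Finally, the figures for omitting provider type say nothing about clinic. Type is already balanced between arms, so leaving it out affects the precision of the test and does not bias it.

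**Conclusion.** The point holds as an unresolved conflict between sections, with a real but bounded consequence. Under 4.1 and 6.3, and with eight PCPs at two sites, the chance of an unequal split of arms by clinic is 0% to 50%, and of complete confounding 0% to 5.6%, according to the unstated provider mix. A 3:1 split shifts the contrast by half of any clinic difference in the analysed outcome. The exposure falls mainly on outcomes without a scheduled baseline, such as SDM-Q-9 and exacerbations, and on any outcome where clinics follow different trends.

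The second, smaller part is that the agreed stratum is only an optional covariate. Omitting it makes the test conservative if provider types differ.

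All figures assume two sites and eight PCPs. The documents also contain three sites and, by section 4.1's own count, 16 PCPs. This should be corrected before the list is generated.

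**What to change.** 1. Settle the number of sites (two in 5.1, three in the synopsis) and of PCPs (eight in 6.3, four plus four per condition in 4.1).
2. State one scheme in 4.1, 6.3 and 9.4.2: blocked randomisation within site, balanced by provider type. With two sites, and if the mix allows, this is one physician and one NP/PA per arm per site (2 × 2 × 2 = 8).
3. Draw any standby replacement from the same site, type and arm.
4. Prespecify provider type as a fixed term in the arm comparison in place of a possible covariate.
5. Keep a coded site and a coded PCP identifier in the analysis data. Section 10.1.2 lists FQHC and clinician among the information excluded from the research database, and without codes neither site adjustment nor the PCP random effect can be fitted.

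**Cost.** The list is generated under a different rule. No extra clinicians are needed if the mix per site permits the layout. Fitting provider type takes between-PCP df from 6 to 5 (critical t 2.447 to 2.571, about 5% higher). Fitting site as well takes it to 4 (2.776, about 13% higher). If type explains nothing, some power is lost: 66% to 62% in the illustration above.
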